## Study Summary

Study title	An Aotearoa-New Zealand (AoNZ) multi-centre, prospective cohort study of acute pancreatitis management and outcomes.
Internal ref. no./ short title	PANORAMA Study
Study design	Multicentre prospective observational cohort study.
Study population	Adult patients diagnosed with acute pancreatitis admitted to any public hospital in AoNZ.
Eligible centres	All public hospitals in AoNZ.
Planned cohort	Enrolment for 3 months.
Objective	To measure adherence to quality performance indicators of the early (<72 hours) management of acute pancreatitis (AP) in AoNZ.
Primary outcomes of interest	
 
• Proportion of patients that were managed in compliance with quality performance indicators overall
 

Secondary outcomes of interest	
 
• Variation in compliance with QPIs between hospitals for each of the management domains
 
• Requirement for mechanical ventilation (invasive and non-invasive)
 
• Requirement for renal replacement therapy
 
• Requirement for inotropic or vasopressor support
 
• Intervention for complication of AP
 
• Alive and discharged at 30-days
 

Follow-up	30-days after admission.
Data collection period	1 July 2024 - 30 September 2024

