# 1. Background and rationale

Acute pancreatitis (AP) is one of the most common gastrointestinal conditions resulting in hospital admission. It has an estimated annual incidence of 58 per 100,000 in Aotearoa-New Zealand (AoNZ) adults (1–3). AP is characterised by a local and systemic inflammatory response with variable clinical progression, from mild to severe as defined by the degree of organ dysfunction (4). The majority of patients with AP suffer only mild disease that is self-resolving. However, 20% develop moderate or severe AP, which involves pancreatic or peripancreatic necrosis, organ failure, or both. Severe pancreatitis is a serious condition with a risk of mortality between 20-40% (5–8). Despite substantial disease burden, there are no effective therapies that alter the course of disease and management remains largely supportive.

In the last decade, a number of landmark clinical trials have provided substantial guidance on the management of the AP, particularly with regards to antibiotic use, endoscopic retrograde cholangiopancreatography (ERCP)(9), and management of necrosis (10,11). Furthermore, multiple scientific bodies have developed and disseminated evidence-based guidelines for managing AP. However, their adoption into clinical practice remains suboptimal. An international cohort study that assessed the compliance rate with current guidelines in the treatment of patients with acute biliary pancreatitis showed a wide variability of practice (12). While it is commonly believed that noncompliance with published guidelines indicates areas in which recommendations are based on insufficient evidence, previous studies have shown a lack of compliance even in areas where randomised controlled trials (RCTs) have already resolved controversial issues during the last 10 years (12,13).

A multicentre national observational study will enable the assessment of compliance to quality performance indicators (QPIs) for the early management of AP in the AoNZ context. Furthermore, it will demonstrate any potential excess morbidity associated with noncompliance to best evidence driven clinical practice. Currently there is no such data for AoNZ. This data can be used to standardise and optimise care nationally to create more equitable outcomes for all patients.

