### Secondary Aims:

- To measure the variation in compliance with QPIs between each hospital in AoNZ for each management domain for the management of AP during the first 72 hours after admission.
- To correlate compliance (overall and for each management domain) with QPIs and defined clinical outcomes stratified by AP severity.
- To compare clinical outcomes between compliant and non-compliant management of patients stratified by AP severity.

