### 4.2. Secondary outcomes

- Variation in compliance with QPIs between hospitals for each of the management domains
- Requirement for mechanical ventilation (invasive and non-invasive)
- Requirement for renal replacement therapy
- Requirement for inotropic or vasopressor support
- Intervention for a complication of AP
- Alive and discharged at 30-days

[figure not shown]

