## 8. Statistical analysis

The study will be reported in accordance with the Strengthening the Reporting of Observational Studies in Epidemiology (STROBE) statement (21). The primary analyses will be descriptive assessments of adherence to unambiguous recommendation in the selected domains of early AP management. Descriptive analysis will be performed where normal continuous variables will be compared via student's t test, and non-normal continuous variables will be compared via Mann-Whitney U test; if >2 categories a one-way ANOVA or Kruskal-Wallis test will be used for normal and non-normal variables respectively, Chi-square tests will be used to detect differences between categorical variables. All analyses will be conducted under a two-tailed hypothesis. Multiple imputation may be used in the case of missing data.

Secondary analyses will evaluate the differences in results according to the hospital. Risk-adjusted funnel plots will be produced to test the performance of individual, anonymised centres for normal rates of primary and selected secondary outcomes. Funnel plots' Y-axes will demonstrate QPI of a management domain and X-axis will show the number of patients admitted in each hospital. Furthermore, differences in clinical outcomes between patients that are managed according to best available evidence (QPI) and those that were not will be explored through mixed effects multivariable logistic models. These models will use the patient at the fixed effect level 1 and the hospital as the random effect level 2 (using the R lmer package) will be performed. A one level, fixed effect binary logistic regression model using a pooled dataset from 5 multiply imputed datasets will also be used in the event of substantial missing data.

Variable selection will be based on statistically significant univariable analysis and those variables deemed clinically significant. Fixed, forced entry will be used to adjust the main outcome measure, The effect of interaction, and sequential removal of non-significant variables will be assessed using changes in Akaike information criteria for multilevel models, and p-values for multiple imputed fixed models.

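### The aim is to measure between-hospital variation in QPI compliance, but the only specific method tests each centre for normal rates and no measure of spread in compliance is specified

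*Protocol*

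**What the plan says.** The secondary aims in Section 2 include "To measure the variation in compliance with QPIs between each hospital in AoNZ for each management domain" over the first 72 hours. Section 4.2 lists the same quantity first among the secondary outcomes: "Variation in compliance with QPIs between hospitals for each of the management domains".

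Section 8 opens its secondary analyses with a general statement that results will be compared by hospital. It then names one specific tool: "Risk-adjusted funnel plots will be produced to test the performance of individual, anonymised centres for normal rates of primary and selected secondary outcomes". The axes are given as follows: "Funnel plots' Y-axes will demonstrate QPI of a management domain and X-axis will show the number of patients admitted in each hospital". On testing in general, Section 8 says "All analyses will be conducted under a two-tailed hypothesis", and it plans chi-square tests for categorical variables.

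A mixed-effects logistic model with hospital as a level 2 random effect is also planned in Section 8. It is for clinical outcomes compared between patients managed according to the QPIs and those who were not. It is not specified for compliance itself.

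**The concern.** To measure variation is to estimate a quantity: how far hospitals' true compliance rates spread around the national rate. A funnel plot asks another question of one hospital at a time, namely whether its observed rate is compatible with a common rate given its volume. The number of hospitals flagged depends on their volumes as well as on the true spread, so the same real variation gives few flags among small hospitals and many among large ones.

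The stated purpose of the plot, a test for normal rates, also invites a conclusion that the test cannot give. A hospital with few patients can be well below the national rate and still lie inside wide limits. Section 1 wants these data to help standardise and optimise care nationally. If unflagged centres were read as normal, practice variation would be understated.

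**Working it through.** **Aim against method.** The target is the between-hospital variation in compliance, per domain (Sections 2 and 4.2). The methods in Section 8 that bear on it are:
- a general comparison by hospital, with no estimator named;
- chi-square tests, which can detect a difference but do not estimate its size;
- funnel plots, which test each centre against a common rate.

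The one model with a between-hospital variance has clinical outcomes as its response. No listed method has spread in compliance as its result.

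**Patients per hospital.** The protocol gives no target sample size or number of hospitals, so there is no planned figure to reproduce. It does give the incidence (Section 1: "It has an estimated annual incidence of 58 per 100,000 in Aotearoa-New Zealand (AoNZ) adults"), the period (Study Summary: "Enrolment for 3 months") and the eligible centres ("All public hospitals in AoNZ"). The adult population (3.5-4.3 million) and the number of hospitals are assumptions.
- Patients = population × 58/100,000 × 0.25.
- 3.5 million gives about 508; 4.3 million gives about 624, if every case is captured.
- With 20-25 hospitals: 508/25 = 20 to 624/20 = 31 per hospital.
- With 15-40 hospitals: 508/40 = 13 to 624/15 = 42 per hospital.

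These are averages. Actual volumes will be unequal.

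**Chance that a low hospital stays inside the limits.** Further assumptions are a national rate of 80%, crude binomial counts, and limits of 95% or 99.8% (the protocol states none). Let X be the number of compliant patients out of n.
- Exact limits: a hospital is flagged low if X ≤ c, where c is the largest value with P(X ≤ c | n, 0.80) ≤ 0.025 (0.001 for 99.8%).
- Normal-approximation limits: flagged low if X/n < 0.80 − z√(0.80 × 0.20/n), with z = 1.96 for 95%.
- Chance of staying inside = P(X > c | n, true rate).

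Example at n = 30 with 95% limits. Exact: P(X ≤ 18) = 0.0095 and P(X ≤ 19) = 0.0256, so c = 18. Normal approximation: 0.80 − 1.96 × √(0.16/30) = 0.657, or 19.7 patients, so c = 19. With a true rate of 65%, P(X > 18) = 65% and P(X > 19) = 51%.

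Chance of staying inside (normal-approximation to exact limits):

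| Limits | n | True 70% | True 65% | True 60% |
|---|---|---|---|---|
| 95% | 20 | 77-89% | 60-76% | 42-60% |
| 95% | 25 | 68-81% | 47-63% | 27-42% |
| 95% | 30 | 73-84% | 51-65% | 29-43% |
| 99.8% | 20 | 95-98% | 88-95% | 76-87% |
| 99.8% | 30 | 92-96% | 78-87% | 58-71% |

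The rates do not fall steadily with n because counts are whole numbers.

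**Larger shortfalls.** At n = 30 with 95% limits, a true rate of 60% is flagged 57-71% of the time. A true rate of 55% is missed 14-23% of the time, and 50% is missed 5-10%.

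**Other national rates.** For national rates of 50-90% and n = 20-30, 95% limits flag a 10-point shortfall 11-39% of the time, a 15-point shortfall 24-65% and a 20-point shortfall 40-84%.

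**Volume needed.** For an 80% chance of a flag at 95% limits, n = [1.96√(p0(1−p0)) + 0.84√(p1(1−p1))]²/(p0−p1)². For 80% against 70% this is (0.784 + 0.386)²/0.01, about 137 patients. For 80% against 60% it is (0.784 + 0.412)²/0.04, about 36.

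**The case against.** The strongest reply is that Section 8 already treats variation descriptively. Each hospital's rate is plotted against its volume, so a low rate is visible whether or not it is flagged, and limits that widen at low volume are how a funnel plot is meant to handle small centres. The choice of limits, interval method or variance measure could be left to a statistical analysis plan, which is not shown here. That stands as far as the limits go, and the point does not rest on them. It does not answer the mismatch: the protocol itself fixes the purpose of the plot as a test, while its aim is to measure.

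Four stronger readings are tempting and are not supported.
- A reader might infer a rule that a centre inside the limits counts as normal. No such rule is written. It is only a natural reading of a test for normal rates.
- A reader might infer that most poorly performing hospitals would be missed. That depends on the size of the shortfall, the limits and the volume. At n = 30 and 95% limits, shortfalls of 20 points or more are flagged more often than not.
- A reader might infer that between-hospital variation is never estimated. The outcome models do carry a hospital random effect, and nothing excludes a later estimate for compliance. What can be said is that none is specified.
- A reader might extend the argument to rare outcomes such as organ support or death. Section 8 speaks only of selected secondary outcomes without naming them, and its axis description mentions only QPIs.

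The calculation also uses crude rates, whereas the plots are to be risk-adjusted. It therefore shows the order of size rather than exact operating characteristics.

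**Conclusion.** The point holds as a mismatch between aim and method. The protocol sets out to measure variation in compliance per domain, specifies a per-centre test for normal rates, and specifies no measure of spread in compliance.

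The size of the problem rests on assumptions outside the protocol: about 20-30 patients per hospital (13-42 over the wider range of hospital numbers), an 80% national rate and conventional limits. Under these, a hospital 10-15 points below the national rate stays inside 95% limits about half the time or more, and inside 99.8% limits more often still. Lying inside the limits is therefore weak evidence that a hospital's rate is normal. Large shortfalls are a different matter, since 95% limits usually detect them at 30 patients.

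**What to change.** Make two changes in Section 8.

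1. Replace the stated purpose of the funnel plots. Suggested wording: *Risk-adjusted funnel plots will display each anonymised centre's rate with its 95% interval. Centres inside the limits will be reported as not shown to differ from the overall rate.*
2. Answer the variation aim directly. Suggested wording: *For each QPI domain, a logistic model of compliance with a random intercept for hospital will be fitted, and the between-hospital standard deviation or median odds ratio will be reported with a 95% interval.* This is the hospital random effect already planned for the clinical outcomes, applied to compliance.

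The cost is a wording change and one extra model per domain on data already being collected. The intervals for the between-hospital spread will be wide, and many small hospitals will receive an inconclusive result.

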## 3. Quality Performance Indicators

Multiple practice guidelines have been published for the management of AP (14–19). The recommendations in these guidelines are usually based on a systematic review of the relevant literature and the evidence on which is based on the available evidence, which is usually graded. Quality performance indicators will be drawn from these evidence-based recommendations for each of the nominated management domains that are relevant to the management of patients within the first 72 hours from admission to hospital. Any differences in the recommendations between the source guidelines will be resolved by discussion amongst the Scientific Advisory Group and consensus established for the QPIs.

The QPIs were developed for the following management domains: (Appendix D: Table 1 with guidelines)

**Table 1.** Quality Performance Indicators

	Domain	QPI	Ref*	Metrics
1	Diagnosis	All patients diagnosed within 12 hours of admission	IAP	RAC criteria for diagnosis: enzymes 3xUL, typical pain ± CT scan
2	Aetiology	All patients had tests for aetiology determined within 24 hours of admission	IAP	U/S for gallstones ETOH history with intake (units per week, timing of binge to pain) If both negative then lipids, IgG4, drugs
3	Severity (predicted)	All patients had prediction of severity on admission	IAP	N / Y, if yes method (drop-down of all options and other) Further drop-down bar will the give options for severity (mild, moderate, and severe)

4	Severity (actual)	All patients had actual severity determined at 48 hours	-	N / Y, if yes method (drop-down RAC, DBC and other) Further drop-down bar will the give options for severity (mild, moderate, and severe)
5	CT scan	Initial CT assessment performed after 72-96 hours if poor response to initial management or clinical deterioration, unless there is diagnostic uncertainty. Not required for severity prediction.	IAP	N / Y, if yes indication (drop-down with other)
6	Transfer	All patients with predicted or actual severe AP in the first 72 hours are discussed with specialist pancreas service.	Nice	N / Y Indication for transfer (drop-down)
7	Analgesia	All patients given narcotic analgesia within one hour of admission	-	Step-up or step-down approach? IV analgesia given on admission N / Y NSAIDS given to mild AP Analgesics prescribed

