8	Fluids	
 
All patients commenced on IV Hartmann's solution within one hour of admission to the emergency department by a clinician and at an initial rate of 5-10 ml /kg in response to hypovolemia until resuscitation goals reached.
 
Then a rate of 1-2 ml/kg/hour for patients not tolerating PO in the first 48 hours.
 
	IAP	IV fluids N / Y Time commenced from admission What initial fluid was given? Initial prescribed rate Initial received rate Average rate 2 nd 24 hours Average rate 3 rd 24 hours Fluid bolus given (# times and and timing) Volume / 24 hours over 72 hours?
9	Anticoagulation	All patients with predicted severe AP considered for or started on anticoagulation within 24 hours of admission	-	Anticoagulation N / Y Medication prescribed When started (hours from admission)
10	Antibiotics	Antibiotic prophylaxis not recommended for the prevention of infectious complications in AP	IAP	Antibiotic N / Y Antibiotic indication

11	Nutrition	
 
1. No patients made 'nil-by-mouth' and no food withheld unless there was a clear reason.
 
2. Offer EN to anyone with MSAP or SAP starting within 72 hrs.
 
3. PN avoided unless EN fails or is contraindicated
 
	NICE	Initial NBM N / Y From admission given trial of light diet. N / Y Initial NG or NJ? EN started within 72 hours if needed N / Y EN prescribed rate PN started if EN was not tolerated or contraindicated.
12	ERCP/ES	ERCP is indicated in patients with biliary pancreatitis and acute cholangitis within 48 hours of admission.	IAP	ERCP N / Y Indication: cholangitis or cholestasis When done? (hours)

\* Reference of guideline from which the QPI is primarily taken from

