Type of opioid prescribed (if any)	Codeine/ Morphine/ Fentanyl/ Tramadol/ Oxycodone/ Other (please specify)/ no opioids prescribed
Date opioid analgesia first administered	Date (dd/mm/yyyy)
Time opioid medication is administered to patient	24 hour clock
Route	PO/ IV
(If regular) daily dose	mg
(If PRN) total dose in first 72 hours	mg

(If yes) Date opioids first administered	Date (dd/mm/yyyy)
(If yes) Time opioid medication first administered as per drug chart?	24 hour clock
Further analgesic modalities	PCA/ ketamine/ local nerve blocks/ other (please specify)
Transfer to different hospital	
Patients with predicted severe disease discussed with specialised pancreas service ( Appendix B ) in first 72 hours from admission	Yes/ No/ not applicable
Patient transferred to a different hospital in the first 72 hours?	Yes/No
(If yes) Date of transfer	Yes/No
(If yes) Location transferred to	List of hospitals
(If yes) Reason for transfer to different hospital?	Severe disease/ requires ERCP/ requires interventional management of local complication/ other (free text)
ERCP	
Cholangitis in first 72 hours ( Appendix F )	Yes/ No
Cholestasis in first 72 hours (radiological + deranged LFTs)	Yes/ No
ERCP performed in the first 72 hours	Yes/ No
Fluid management*	
Baseline variables	
Bag 1	
Date of administration	Date (dd/mm/yyyy)
Time of administration	Time (24-hour)
Volume administered	Volume (ml)
How long does fluid run for?	Time (hours)
Type of fluid	0.9% Normal saline/ Hartmann's/ plasmalyte/ colloid/ 0.45 saline + dextrose/ 0.18 saline + dextrose/ other (please specify)
Further administration of intravenous fluid (IVF) in the first 3 days of admission? ( Appendix B )	Yes/no
Bag 2	
Date of administration	Date (dd/mm/yyyy)
Time of administration	Time (24-hour)

Volume administered	Volume (ml)
Time fluid is administered	Time (hours)
Type of fluid	0.9% Normal saline/ Hartmann's/ plasmalyte/ colloid/ other (please specify)
Further administration of intravenous fluid (IVF) in the first 2 days of admission?	Yes/no
Documented fluid review after 12 hours ( $\pm$ 4 hours)	Yes/no
Documented fluid review after 24 hours ( $\pm$ 4 hours)	Yes/no
Documented fluid review after 48 hours ( $\pm$ 4 hours)	Yes/no
Documented fluid review after 72 hours ( $\pm$ 4 hours)	Yes/no
Early Nutritional support	
On admission patient kept nil by mouth (NBM)	Yes/no

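### Funnel plots put admissions on the X-axis for every management domain, but QPIs 6, 9 and 12 apply only to subgroups, so for these the axis does not measure the precision of the plotted rate

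*Protocol*

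**What the plan says.** Protocol section 8 (Statistical analysis) gives the purpose of the plots: "Risk-adjusted funnel plots will be produced to test the performance of individual, anonymised centres for normal rates of primary and selected secondary outcomes". The next sentence puts a domain's indicator on the vertical axis and fixes the horizontal one: "X-axis will show the number of patients admitted in each hospital". The same horizontal axis serves every domain. Section 8 states no control-limit formula and no limit level; it says only that "All analyses will be conducted under a two-tailed hypothesis".

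Section 4.2 lists between-hospital variation in compliance, domain by domain, as the first secondary outcome.

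Table 1 in section 3 restricts several indicators to subgroups:

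- QPI 6 (Transfer): "All patients with predicted or actual severe AP in the first 72 hours are discussed with specialist pancreas service".
- QPI 9 (Anticoagulation): "All patients with predicted severe AP considered for or started on anticoagulation within 24 hours of admission".
- QPI 12 (ERCP/ES): "ERCP is indicated in patients with biliary pancreatitis and acute cholangitis within 48 hours of admission".
- QPI 11 (Nutrition), part 2 only: patients with moderately severe or severe disease. Part 1 of the same domain applies to everyone.

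Other indicators, such as QPI 1 on time to diagnosis, are worded for all patients.

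In section 5.5 the data item for QPI 6 has the options "Yes/ No/ not applicable". No general rule says how patients outside an indicator's subgroup are scored.

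**The concern.** The horizontal axis of a funnel plot is its precision scale: limits narrow as it increases. It therefore has to be the number of patients behind the plotted proportion. For an indicator that applies to all patients, admissions are that number. For one that applies to a subgroup, the observed rate rests on far fewer patients than the axis shows.

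These plots are meant to judge individual centres and bear on the first secondary aim. If limits were drawn at the admission count, chance variation in small eligible groups could be read as real differences in care between hospitals.

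**Working it through.** The protocol gives no funnel limit, hospital volume or expected compliance, so there is no figure of its own to reproduce.

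**Inputs.**
- Axis: admissions per hospital (section 8).
- Eligible share f: section 1 puts moderate or severe disease at 20%. This is a direct anchor only for QPI 11 part 2. The shares for QPIs 6, 9 and 12 are not given, so 20% is illustrative for them.
- Assumed: compliance p, admissions N, eligible m = f × N, and limits at 95% (z = 1.96) or 99.8% (z = 3.09).
- Every hospital is taken to have the same true compliance p, so any flag is false. Limits are unadjusted.

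**Case A: compliance scored on eligible patients, limits drawn at admissions.**

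Limits drawn: p ± z√(p(1−p)/N). Limits needed: p ± z√(p(1−p)/m). Ratio of widths: √(N/m) = √(1/f).

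Probability that an average hospital is flagged, by normal approximation: 2 × [1 − Φ(z√f)].

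At f = 0.20, √(1/0.20) = 2.24. Then z√f = 0.877 at 95%, giving 38.1%, and 1.382 at 99.8%, giving 16.7%.

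| Eligible share | Too narrow by | Outside 95% limits | Outside 99.8% limits |
|---|---|---|---|
| 100% | 1.00 | 5.0% | 0.2% |
| 50% | 1.41 | 16.6% | 2.9% |
| 20% | 2.24 | 38.1% | 16.7% |
| 10% | 3.16 | 53.5% | 32.8% |
| 5% | 4.47 | 66.1% | 49.0% |

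**Exact binomial check (p = 70%, N = 60, m = 12).** Limits at N: 0.70 ± 1.96√(0.21/60) = 58.4% to 81.6%. With 12 eligible patients, only 8 or 9 compliant (66.7% or 75.0%) fall inside. Their probability is 0.2311 + 0.2397 = 0.471, so 52.9% of average hospitals fall outside. Limits at m: 0.70 ± 1.96√(0.21/12) = 44.1% to 95.9%. Counts of 6 to 11 are then inside, and 5.2% fall outside.

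Two further cases at 95%:
- p = 70%, N = 30, m = 3: 55.9% outside limits at N, 2.7% outside limits at m.
- p = 80%, N = 100, m = 20: 40.2% and 4.4%.

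With so few eligible patients the exact figure jumps with the inputs. At p = 90% and m = 5 it is 100% for N = 50 but 8.1% for N = 30. In the latter case limits at m give the same 8.1%.

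**Case B: patients outside the subgroup counted as compliant over all admissions.**

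The plotted rate becomes 1 − f + f × p, with denominator N, so the axis fits. False flags in the three examples above (m = 12, 3 and 20) are 0.9%, 2.7% and 4.4%. But at f = 0.20 and p = 0 the plotted rate is 1 − 0.20 = 80%: a hospital that failed every eligible patient would appear 80% compliant.

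**The case against.** The strongest reply is that section 8 says only what the axis shows, not how limits are computed. Limits could use eligible counts, and that detail may properly sit in an analysis plan that is not shown here. This stands as far as it goes: a reader might infer that the plots as written will flag average hospitals, and the document does not establish that. It does not rescue the sentence. With limits from eligible counts, two hospitals with equal admissions but different eligible numbers need different limits, so no single funnel can be drawn on the stated axis.

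A second reply is that patients outside the subgroup may be counted as compliant. The false flags then disappear, as Case B shows, but the indicator is diluted. The not-applicable option for QPI 6 points to eligible-only scoring for that item; it settles nothing for QPIs 9 or 12.

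Three further points stand:
- QPI 11 part 2 is affected only if plotted on its own, which the protocol does not say.
- The plots are to be risk-adjusted, whereas the calculation uses unadjusted limits. Adjustment changes the expected rate, not the number of patients behind the observed one, so the axis problem remains. Any remedy must still fit the adjusted plot.
- A reader might want one overall range for the false-flag rate. The jumps between neighbouring inputs show that such a range would depend on the values chosen, and most of the inputs are assumptions.

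**Conclusion.** The axis is wrongly specified for QPIs 6, 9 and 12, and for QPI 11 part 2 if plotted separately. That follows from section 8 and Table 1 alone.

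The size depends on how the limits and non-applicable patients are handled. If limits follow the stated axis and scoring is on eligible patients, a 20% share gives limits 2.24 times too narrow, with about 38% of average hospitals outside 95% limits and 17% outside 99.8% limits, against a nominal 5% and 0.2%. Only the 20% figure comes from the protocol, where it describes moderate or severe disease; compliance, volumes and limit levels are assumptions.

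Indicators that apply to every patient are not affected, and neither the primary outcome nor the mixed models rest on this axis. It should be fixed, but as a secondary display that can be corrected at analysis it is not a critical fault.

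**What to change.** Replace the axis sentence in section 8 with:

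> For each QPI, the X-axis and the control limits use the number of patients at that hospital to whom the QPI applies; patients to whom it does not apply are excluded from numerator and denominator. Limits are exact binomial where the plot is unadjusted, and are based on the same eligible patients where it is risk-adjusted.

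For QPIs that apply to every patient this number is the number admitted, so those plots stay as planned.

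The cost is one sentence and no further data collection. The downside is that plots for conditional indicators will have wide limits and flag fewer centres. In the example with 12 eligible patients the 95% limits by normal approximation run from 44.1% to 95.9%, which reflects how little such a plot can say about a single hospital.
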